6.1 Investigational Product

Selpercatinib will be provided in a capsule in 40 mg and 80 mg dose strengths.

6.1.1 Capsules

Selpercatinib will be provided in a capsule in 40 mg and 80 mg dose strengths. The 40 mg capsules will be provided to the sites in bottles of 60 capsules/bottle. The 80 mg capsules will be provided to the sites in bottles of 120 capsules/bottle. The site pharmacist will dispense bottles to the patient in an amount necessary to allow for outpatient administration at the assigned dose level. Dosing is intended to be fixed (i.e., not weight-based or body surface area-based).

Selpercatinib gelatin capsules are to be stored at controlled room temperature in accordance with the labeled storage conditions.

Additional details regarding the investigational product are provided in the selpercatinib Pharmacy Manual and the selpercatinib IB.

6.2 Selpercatinib Administration

6.2.1 General Dosing Instructions

Selpercatinib doses will be administered at approximately the same times on each day and BID dosing will be separated by approximately 12 hours (a minimum of 6 hours between consecutive doses).

The patient will keep a daily diary to record dosing compliance, which will also be assessed at each clinic visit by means of a capsule count in the returned bottle(s). Late doses (i.e., 4 or more hours after scheduled time) should be noted in the diary. Doses that are late by more than 6 hours should be skipped and recorded in the dosing diary as missed. Vomiting after dosing should be noted in the diary and a vomited dose should not be re-dosed or replaced.

Selpercatinib may be given with or without food, unless the patient requires treatment with PPIs, H2 receptor antagonists, or locally-acting antacids. Additional guidance is provided in Section [6.3.3](#).

Patients taking these agents are encouraged to record the time of each dose in relationship to each dose of selpercatinib in the dosing diary (inaccurate recording will not be considered a protocol violation).

6.2.2 Cycle 1

Patients will begin dosing on C1D1. Serial blood samples for intensive PK monitoring will be collected for a total of 12 patients, blood samples for population pharmacokinetic (PopPK) will be collected for all enrolled patients, and the patient will be monitored for safety as outlined in Section 7.2. Cycle length is 28 days for all patients.

6.2.3 Cycles 2 and Higher

Patients will receive selpercatinib 160 mg BID in continuous 28-day cycles until PD, unacceptable toxicity, or other reasons for treatment discontinuation. Patients with documented PD may be allowed to continue selpercatinib if the patient is tolerating treatment and, in the opinion of the Investigator, the patient is deriving clinical benefit from continuing study treatment, and continuation of treatment is approved by the Sponsor. Additionally, the patient must re consent prior to continuing to receive study treatment.

6.2.4 Dose Delays and Modifications

Cycles are 28 days in duration regardless of dose interruption unless toxicity recovery period before entering next cycle includes Day 1 of the next cycle. For patients with dose interruption, next cycle will start with resumption of study drug. In this situation, disease assessments should continue to follow the original schedule.

For all parts of this study, toxicities such as nausea, vomiting, or diarrhea or dizziness or dehydration related to these symptoms, may be managed with increased supportive care, including hydration, electrolyte repletion and the use of anti-emetics such as serotonin type 3 (5-HT3) antagonists and/or anti-diarrheals such as loperamide as appropriate.

Treatment for the first cycle should commence only if all the inclusion and exclusion criteria are met. Subsequently, the selpercatinib dose may be delayed/modified if the patient experiences a Grade 3 or greater clinical AE considered to be at least possibly related to selpercatinib.

Dose reductions should be made according to the following parameters using the dose reduction table below.

- Interrupt dosing for CTCAE v5.0 Grade 3 or greater adverse events or Grade 2 adverse events not resolved within 48 hours with appropriate supportive care (e.g., nausea not improved with antiemetics) and considered intolerable by the patient or the investigator.
- For selpercatinib related specific adverse events (hypersensitivity, liver function test abnormalities, thrombocytopenia, and hypertension), see dose adjustments below in Sections 6.2.3 (any concerns of these recommended actions in clinical practice should be discussed with the Sponsor, who may permit adjust actions).
- Dose modifications for ECG changes are described in Section 8.2.1. If a patient receiving selpercatinib experiences QTCF > 500 msec despite two dose reductions and if the investigator deems it in the best interest of the patient, the patient may continue treatment with study drug with CRP/CRS approval. In addition, Lilly may request a copy of the ECGs for adjudication.
- Upon resolution (or return to patient's baseline) of adverse events at least possibly related to treatment, reduce the dose as follows:
 - If previously receiving dose level 1, resume treatment at dose level -1
 - If previous receiving dose level -1, resume treatment at dose level -2
 - If previously receiving dose level -2, resume treatment at the same dose level. If a second AE requiring dose modification occurs at dose level -2, discontinue study treatment.
 - For AEs clearly unrelated to study treatment that resolve or return to patient's baseline in ≤14 days, dose reduction is not required.
 - Re-escalation to a prior dose level after a dose reduction is not permitted (other than hypersensitivity, liver test abnormalities, thrombocytopenia, and hypertension).

Permanently discontinue treatment for any of: malignant hypertension, hypertensive crisis, or persistent uncontrolled hypertension despite optimal medical management. Patients with clinical benefit who experience recurrent hypersensitivity reaction or recurrent AST or ALT increase despite dose reductions should be discussed with the CRS/CRP and may be allowed to continue treatment with more than 2 dose reductions if continuation is considered to be safe and in their best interest.

Before the start of each cycle, Grade 3 hematologic toxicity possibly related to selpercatinib must resolve to either baseline or at least Grade 2. If a patient experiences Grade 4 hematologic toxicity possibly related to selpercatinib, then dosing must be suspended (until the toxicity resolves to either baseline or at least Grade 2) and the dose of selpercatinib must be reduced as outlined in [Table 6-1](#).

Before the start of each cycle, nonhematologic toxicity (except AEs with no immediate medical consequence that can be controlled with adequate treatment (e.g. pain, alopecia, neuropathy fatigue, nausea, vomiting, diarrhea, Grade 2 hypothyroidism, or Grade 2 hypertension).) possibly related to selpercatinib must resolve to either baseline or at least Grade 1. If a patient experiences persistent or recurrent Grade 2 nonhematologic toxicity possibly related to selpercatinib that does not resolve with maximal supportive measures within 7 days to either baseline or Grade 1, then dosing may be suspended (until the toxicity resolves to either baseline or at least Grade 1) and the dose of selpercatinib may be reduced as outlined in [Table 6-1](#).

Treatment may be delayed for a maximum of 28 days to allow a patient sufficient time for recovery from selpercatinib-related toxicity. If a patient does not recover from the toxicity within 28 days from the time of last treatment, the patient must be discontinued from selpercatinib. In rare circumstances, a delay >28 days may be permitted before discontinuing the patient from treatment, as long as the patient demonstrates clinical benefit without objective progression and is recovering from the toxicity. Such circumstances should be discussed between Sponsor and Investigator and documented.

Table 6-1 Suggested Toxicity Management for all Parts of this Study

| Dose Level | Dose of Selpercatinib |
|---------------------------------|---|
| Starting Dose | 160 mg BID |
| First Dose Reduction | 120 mg BID* |
| Second Dose Reduction | 80 mg BID* |
| Third Dose Reduction and Beyond | Only permitted if there is a compelling clinical rationale articulated by the Investigator and approved by the Sponsor. |

Abbreviations: AE-adverse events; BID-twice daily; LFT-liver function test.

*For the specific AEs of hypersensitivity reactions, LFT increases, thrombocytopenia and hypertension, the Sponsor may recommend a lower starting dose (i.e. 40 mg BID for hypersensitivity reactions and 80 mg BID for certain LFT increases, 120 mg BID for thrombocytopenia) upon resumption of study drug treatment, with subsequent dose escalation if tolerated without clinically significant recurrence of the AEs. Occurrence of these AEs should be discussed with the Sponsor.

All dose interruptions and dose modifications and the reasons for those changes will be recorded in the electronic Case Report Form (eCRF).

Guidance for Investigator on Specific Adverse Events

Dose Modifications for Selpercatinib Hypersensitivity

Please refer to the IB for the most current guidance on management of selpercatinib hypersensitivity reactions. Recommended actions are shown below.

If selpercatinib drug hypersensitivity is suspected, study drug should be withheld and treatment with steroids at 1 mg/kg prednisone (or equivalent) should be initiated. Upon resolution, selpercatinib may be resumed at a reduced dose of 40 mg BID while continuing steroids at the same dose. Note that this dose reduction does not require sponsor approval. Hypersensitivity has recurred in some patients, typically at 3 to 6 hours following drug administration. Follow the guidelines below if hypersensitivity recurs:

- If recurrence is severe, selpercatinib should again be withheld.
- If recurrence is mild (e.g., isolated instances of rash or myalgias or low-grade fever), selpercatinib may be continued cautiously, together with treatment with supportive therapy (e.g., topical treatments, ibuprofen).
- If the patient experiences a clinically significant recurrence of drug hypersensitivity at the initial re-exposure dose of 40 mg BID, selpercatinib should be discontinued.

After a minimum of 7 days and in the absence of clinically significant recurrent drug hypersensitivity, the dose of selpercatinib may be escalated sequentially to 80 mg BID, 120 mg BID, and 160 mg BID. Once the patient has tolerated treatment for a minimum of 7 days at the final dose, steroids may be tapered slowly.

Dose Modifications for Selpercatinib Related Liver Function Test Abnormalities

If a patient experiences \geq Grade 3 elevated liver function tests (LFTs; including AST, ALT, ALP and total and direct bilirubin), study drug should be withheld and evaluation for potential alternative causes should be conducted (e.g., history of other hepatotoxic medications/substances, viral serologies, liver imaging). A repeated value 3 to 5 days after the initial finding of elevation of LFTs should be obtained to confirm the abnormality and to confirm if it is increasing or decreasing. Thereafter, LFTs should be monitored at least weekly until resolution to normal/baseline (depending on the clinical situation, resolution to Grade 1 if baseline is acceptable but waiting until normalization is preferable). If the LFT abnormalities do not begin to resolve (or worsen) within 5 days of the AE, a hepatology consultation should be considered to evaluate the need for a liver biopsy.

Upon resolution, for patients who received 160 mg BID or 120 mg BID, the selpercatinib dose should be reduced by 2 dose levels (80 mg BID or 40 mg BID, respectively) with weekly LFTs monitoring. In the absence of recurrent LFT abnormalities, the dose of selpercatinib may be escalated sequentially to the next highest dose (120 mg BID or 80 mg BID, respectively) after a minimum of 2 weeks and again to the original dose and after a minimum of an additional cycle. Once the patient has been treated at a stable dose of selpercatinib for a minimum of 1 cycle without recurrent LFT abnormalities, the frequency of LFTs monitoring may be decreased (e.g., midcycle for 2 cycles and then at the start of every cycle thereafter).

For patients who experience \geq Grade 3 elevated LFTs at 80 mg BID, the sponsor should be contacted for additional guidance regarding dose modification. If the patient experiences \geq Grade 3 elevated LFTs at a dose of 40 mg BID, selpercatinib should be discontinued. Please refer to Section 8.2.2 for additional monitoring that may need to be initiated.

Dose Modifications for Thrombocytopenia

If a patient is discovered to have thrombocytopenia \geq Grade 3, study drug should be withheld, and the patient should be evaluated for alternative causes (medications/substances, viral studies). A hematology consultation may be considered, as necessary, to understand the etiology and to consider a role for concomitant steroid therapy. The patient should undergo weekly complete blood count (CBC) testing until the event resolves and CBC level returns to normal/baseline. Upon recovery, the patient should resume selpercatinib with a dose reduction of at least 1 level with weekly CBC surveillance for 1 full cycle.

Dose Modifications for Hypertension

Hypertension is defined as:

- a sustained increase in blood pressure from baseline, as evidenced by ≥ 2 readings on ≥ 2 separate occasions, or
- a clinically significant elevation requiring acute treatment.

If hypertension occurs, study drug may be interrupted at the discretion of the investigator while:

- a new antihypertensive medication regimen is initiated, or
- a preexisting regimen is optimized to a reproducible reading of $\leq 140/90$ mmHg.

If study drug is interrupted, it may be resumed at the same or a lower dose at the discretion of the investigator. In all cases, the patient should continue to undergo regular blood pressure monitoring to ensure adequate blood pressure control. Dose re-escalation to the patient's original dose can be considered once adequate blood pressure (BP) control has been obtained; with clinically appropriate monitoring.

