1.6.1 Known and Anticipated Risks

As of a clinical data cut-off (March 30, 2020) for the LIBRETTO-001 first-in-human (FIH) dose finding study, the following TEAEs occurred in $\geq 15\%$ of patients (regardless of attribution to study drug):

- Dry mouth (39.7% total; 35.2% related)
- Diarrhea (38.2% total; 21.8% related)
- Hypertension (36.3% total; 25.1% related)
- AST increased (31.9% total; 25.9% related)
- ALT increased (31.5% total; 25.9% related)
- Fatigue (30.8% total; 19.2% related)
- Constipation (26.6% total; 12.8% related)
- Edema peripheral (25.3% total; 14.1% related)
- Nausea (23.3% total; 10.1% related)
- Headache (23.3% total; 8.6% related)
- Blood creatinine increased (20.2% total; 11.6% related)
- Abdominal pain (19.5% total; 5.9% related)
- Rash (18.1% total; 11.3% related)
- Electrocardiogram QT prolonged (17.5% total; 13.6% related)
- Cough (15.9% total; 1.1% related)
- Vomiting (15.9% total; 4.3% related)
- Dyspnea (15.2% total; 1.6% related)

Additional details are provided in the selpercatinib IB.

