- All prior local treatments for CNS disease (e.g. surgery, whole brain radiation [WBRT], SRS), the start and stop dates for each prior local therapy, the specific lesions treated (if SRS and/or surgery), whether the patient developed intracranial progression after the last prior local treatment, and which lesions progressed since completion of the local therapy must be documented.
27. Clinically significant active cardiovascular disease or history of myocardial infarction within 6 months prior to planned start of selpercatinib or prolongation of the QT interval corrected for heart rate using Fridericia's formula (QTcF) > 470 msec. Correction of suspected drug-induced QTcF prolongation may be attempted at the investigator's discretion if clinically safe to do so.
 28. History of Human Immunodeficiency Virus (known HIV 1/2 antibodies positive); patients with unknown HIV status do not need to be tested.
 29. History of active hepatitis B (known positive hepatitis B surface antigen [HbsAg] and quantitative hepatitis B DNA greater than the upper limit of detection of the assay) or C (known positive hepatitis C antibody and quantitative hepatitis C RNA greater than the upper limit of detection of the assay); patients with unknown hepatitis B/hepatitis C status do not need to be tested.
 30. Active uncontrolled systemic bacterial, viral, or fungal infection or serious ongoing intercurrent illness, such as hypertension or diabetes, despite optimal treatment. Screening for chronic conditions is not required.
 31. Clinically significant active malabsorption syndrome or other condition likely to affect gastrointestinal absorption of the study drug.
 32. Uncontrolled symptomatic hyperthyroidism or hypothyroidism.
 33. Uncontrolled symptomatic hypercalcemia or hypocalcemia.
 34. Concurrent use of drugs known to prolong QTc (refer to [Appendix D](#) of the main protocol)
 35. Pregnancy or lactation. Breast-feeding should be interrupted when selpercatinib is started; breast-feeding can be resumed 3 months after discontinuation of selpercatinib.
 36. Active second malignancy other than minor treatment of indolent cancers with prior sponsor approval.

5 Enrollment Procedures

For all patients, a copy of the redacted Molecular Pathology Report, or other report(s) describing tumor *RET* (and/or other) alteration analysis must be submitted to the Sponsor or designee during Screening for review prior to patient enrollment.

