6.3.2 Allowed Concomitant Medications

Standard supportive medications may be used in accordance with institutional guidelines and Investigator discretion. These may include hematopoietic growth factors to treat neutropenia, anemia or thrombocytopenia (in countries where hematopoietic growth factors are approved for use) in accordance with American Society for Clinical Oncology guidelines (but not for prophylaxis in C1); RBC and platelet transfusions, anti-emetic, analgesic and antidiarrheal medications; electrolyte repletion (e.g., calcium and magnesium) to correct low electrolyte levels; conditional use of steroids treatment as indicated in Section 6.3.3; thyroid replacement therapy for

hypothyroidism; and bisphosphonates, denosumab; and other medications for the treatment of osteoporosis, prevention of skeletal-related events from bone metastases, and /or hypoparathyroidism. Continuation of standard of care medications, including adjuvant hormonal therapy for patients with prostate cancer (e.g., gonadotropin-releasing hormone [GnRH] or luteinizing hormone-releasing hormone [LHRH] agonists) and breast cancer (e.g., GnRH/LHRH agonists, aromatase inhibitors, selective estrogen receptor modulators [SERMs] or degraders [SERDs]), that the patient has been on for the previous 28 days, are allowed, provided they are not on the list of prohibited concomitant medications (refer to Section 6.3.3 and Appendix D).

Local treatment while receiving selpercatinib (e.g., palliative radiation therapy or surgery for bone metastases) is permitted with Sponsor approval; however, the Sponsor recommends holding selpercatinib for approximately 5 half-lives (approximately 2 to 3 days) before and after radiation therapy or surgery. Any concern for disease flare due to a prolonged period off from selpercatinib should be discussed with the Sponsor, who may permit holding selpercatinib for a shorter period of time.

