6.3.3 Other Concomitant Medications

As selpercatinib is a substrate of CYP3A4, patients should avoid taking strong or moderate inhibitors or inducers of CYP3A4 as they could alter the drug's PK. If concomitant use of strong and moderate CYP3A inhibitors cannot be avoided, reduce the selpercatinib dosage and monitor the QT interval with ECGs more frequently.

Since selpercatinib is more soluble in an acidic environment than a neutral one, absorption may be impacted by stomach acidity, and concomitant use of pH altering agents require additional instructions. The concomitant use of PPIs should be avoided, and patients must take selpercatinib with food (at least 400 calories) when coadministered with a PPI if concomitant use cannot be avoided (refer to Appendix E).

When concurrent use of an H2 blocking agent is necessary, e.g., ranitidine (Zantac[®]), famotidine (Gaster[®]), or cimetidine (Tagamet[®]), it must be administered only 10 hours before or 2 hours after the dose of selpercatinib.

When concurrent use of an antacid is necessary, e.g., aluminum hydroxide/magnesium hydroxide/simethicone (Maalox[®]) or calcium carbonate (TUMS[®]), it must be administered 2 hours before and/or 2 hours after the dose of selpercatinib.

Chronic treatment (>7 days) with steroids is not permitted except to treat symptoms from an immune-related AE or brain metastases. Intermittent use of inhaled steroids for asthma or local steroid injections is allowed. Similarly, limited use of systemic corticosteroids (≤7 days) is permitted where it is considered SOC (e.g., as premedication for contrast allergy or for chronic obstructive pulmonary disease exacerbation). Replacement doses of steroids (e.g., prednisone 10 mg daily) are permitted while on study.

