Appendix D Inhibitors and Inducers of CYP3A4

Note: Avoid concomitant use of strong and moderate CYP3A inhibitors or inducers with selpercatinib. If concomitant use of strong and moderate CYP3A inhibitors cannot be avoided, reduce the selpercatinib dosage and monitor the QT interval with ECGs more frequently.

Table 11-4 Examples of Inhibitors of CYP3A4

| Strong inhibitors^a | Moderate inhibitors^b |
|--------------------------------------|--|
| Boceprevir | amprenavir |
| Clarithromycin | aprepitant |
| Conivaptan | atazanavir |
| grapefruit juice | ciprofloxacin |
| Indinavir | darunavir |
| Itraconazole | diltiazem |
| Ketoconazole | erythromycin |
| Lopinavir | fluconazole |
| Mibefradil | fosamprenavir |
| Nefazodone | imatinib |
| Nelfinavir | verapamil |
| Posaconazole | |
| Ritonavir | |
| saquinavir | |
| telaprevir | |
| telithromycin | |
| voriconazole | |

Abbreviations: CYP3A4 = cytochrome P450 3A4.

^a Increases the area under the curve (AUC) of the substrate by ≥ 5 -fold.

^b Increases the AUC of the substrate by 2- to 5-fold.

Table 11-5 Examples of Inducers of CYP3A4

| Strong inducers^a | Moderate inducers^b |
|------------------------------------|--------------------------------------|
| avasimibe | Bosentan |
| carbamazepine | Efavirenz |
| enzalutamide | Etravirine |
| phenytoin | Modafinil |
| rifampin | Nafcillin |
| St John's wort | |

Abbreviations: CYP3A4 = cytochrome P450 3A4.

^a Increases the area under the curve (AUC) of the substrate by \geq 5-fold.

^b Increases the AUC of the substrate by 2- to 5-fold.

Note: The above lists are not exhaustive. See also:

<http://www.fda.gov/drugs/developmentapprovalprocess/developmentresources/druginteractionslabeling/ucm093664.htm>.

http://www.jp-orangebook.gr.jp/cgi-bin/search/search_e.cgi.

| Examples of Agents Known to Cause QTc Prolongation | |
|---|-------------------------------------|
| amiodarone | ibogaine |
| anagrelide | ibutilide |
| azithromycin | levofloxacin |
| chloroquine | levomepromazine (methotrimeprazine) |
| chlorpromazine | levosulpiride |
| cilostazol | methadone |
| ciprofloxacin | moxifloxacin |
| citalopram | ondansetron |
| clarithromycin | papaverine HCl (intracoronary) |
| cocaine | pentamidine |
| disopyramide | pimozide |
| dofetilide | procainamide |
| domperidone | propofol |
| donepezil | quinidine |
| dronedarone | roxithromycin |
| droperidol | sevoflurane |
| erythromycin | sotalol |
| escitalopram | sulpiride |
| flecainide | sultopride |

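### QT-listed drugs are barred at entry, but on treatment 5-HT3 anti-emetics are suggested without a QT condition, and starting 41 of the 45 listed drugs, ondansetron included, triggers no required ECG

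*Protocol*

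**What the plan says.** **At entry.** Protocol section 4.2, criterion 34, excludes "Concurrent use of drugs known to prolong QTc" and refers to Appendix D. The QT table there gives example agents in two columns; one row reads "citalopram | ondansetron". The table says it is not exhaustive and directs the reader to an external current list.

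**On treatment.** Section 6.2.4 says that nausea, vomiting, diarrhea and related dehydration may be managed with supportive care, including "the use of anti-emetics such as serotonin type 3 (5-HT3) antagonists and/or anti-diarrheals such as loperamide as appropriate". Section 6.3.2 allows "RBC and platelet transfusions, anti-emetic, analgesic and antidiarrheal medications" under institutional guidelines and investigator discretion. Neither sentence mentions QT or ECGs. Section 6.3.2 also lets patients continue standard-of-care drugs already taken for 28 days, "provided they are not on the list of prohibited concomitant medications (refer to Section 6.3.3 and Appendix D").

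**ECGs tied to a co-medication.** The only such instruction is in section 6.3.3, repeated in Appendix D: "If concomitant use of strong and moderate CYP3A inhibitors cannot be avoided, reduce the selpercatinib dosage and monitor the QT interval with ECGs more frequently".

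**ECG schedule.** Table 7-1, its note k, and sections 7.2 and 7.3 require ECGs at screening, C1D1, C1D8, Day 1 of Cycles 2 to 6, every 12 weeks after that, and at end of treatment. Section 7.3 permits further ECGs if clinically indicated.

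**The concern.** Selpercatinib prolongs QT in some patients. In the first-in-human study, section 1.6.1 reports QT prolongation in 17.5% of patients (13.6% related), and section 1.5 gives Grade 3-4 rates of 4.0% (2.8% related). The protocol has its own rule for holding the dose when QTcF exceeds 500 msec.

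Against that background, it treats a co-administered QT drug as a reason to exclude a patient, then on treatment suggests a drug class with a member on its own QT list, with no caution. The suggestion arises in patients with vomiting, diarrhea or dehydration, when electrolytes may also be disturbed; note k and section 8.2.1 ask for potassium, magnesium and calcium to be checked when QTcF is high. At stake is how long a drug-induced QT change could go unrecorded, and whether sites handle it alike. No efficacy endpoint or analysis depends on it.

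**Working it through.** **Step 1. Reproduce the ECG calendar.** Cycle length is 28 days (section 6.2.2), so Day 1 of cycle *n* falls on study day 1 + 28 × (*n* − 1). After C6D1, ECGs are 12 × 7 = 84 days apart. Scheduled on-treatment ECG days are 1, 8, 29, 57, 85, 113, 141, 225, 309.

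| Interval | Arithmetic | Nominal gap (days) | Longest gap with ±2-day window at both ends |
|---|---|---|---|
| C1D8 to C2D1 | 29 − 8 | 21 | 25 |
| Consecutive ECGs, C2D1 to C6D1 | e.g. 57 − 29 | 28 | 32 |
| C6D1 to next ECG | 225 − 141 | 84 | 88 |

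The nominal gap is the longest wait for a drug started just after a scheduled ECG. Table 7-1 has no ECG at C1D15 or C1D22.

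**Step 2. Ask which listed drugs trigger an earlier ECG.** The QT table has 23 rows with one empty cell: 23 × 2 − 1 = 45 agents. Set against the strong and moderate inhibitors in Table 11-4, four names appear in both: ciprofloxacin, clarithromycin, erythromycin and fluconazole. For these, section 6.3.3 already asks for more frequent ECGs, though it sets no timing. That leaves 45 − 4 = 41 with no drug-triggered ECG. Ondansetron is among the 41.

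**Step 3. Look for any other on-treatment control.**
- The concomitant drugs that section 6.3.3 disallows or restricts do not include QT drugs as such.
- The proviso in section 6.3.2 that calls Appendix D a prohibited list belongs to the sentence on continued standard-of-care drugs. A newly started anti-emetic is not covered by it.
- The QTcF rules (note k, section 8.2.1) act on an ECG already taken. A QTcF of 481-500 msec calls for one additional ECG that day; above 500 msec calls for repeats, and only there are concomitant medications to be reviewed.
- Chemistries, which include potassium, magnesium and calcium (Appendix H), are taken at C1D8, C1D15 and Day 1 of each cycle. They track electrolytes but not the QT interval.

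**Step 4. Check the obvious substitute.** A site steering away from ondansetron might turn to aprepitant. In Table 11-4 the row "Clarithromycin | aprepitant" puts aprepitant in the moderate-inhibitor column, so it falls under the CYP3A restriction. Advice on anti-emetics therefore has to point away from both lists.

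**The case against.** Criterion 34 governs eligibility, and section 6.2.4 is permissive guidance naming a class. Ondansetron is the only 5-HT3 antagonist named in the QT table, so a site can follow 6.2.4 without using a listed drug. Scheduled ECGs, frequent chemistries, the QTcF rules, recorded concomitant medications and discretionary ECGs are all in place. Further risk detail is deferred to the Investigator's Brochure, which was not available here.

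Most of this stands, and it limits the point. A reader might infer three stronger things that the documents do not support:

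- *That the protocol prescribes a drug it prohibits on treatment.* The entry bar is not an on-treatment ban, and the section 6.3.2 proviso covers continued drugs only. If a site did read that proviso as a general ban, it would clash with 6.2.4 for ondansetron, which is itself a reason to clarify it.
- *That no listed QT drug prompts an ECG.* Four of the 45 do, as CYP3A inhibitors.
- *That the first-in-human rates measure the harm.* Nausea at 23.3% (10.1% related) and the QT rates are background figures across mixed doses. None is attributed to a co-medication or a late ECG.

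What does not stand is the reply that investigator judgment is enough. The sponsor wrote an explicit ECG instruction for CYP3A inhibitors instead of relying on judgment, and nothing in 6.2.4 tells a site to choose an unlisted anti-emetic. The brochure may cover this, but the protocol text would still lack the condition.

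**Conclusion.** The point holds in limited form, as a cheap improvement to patient safety. Section 6.2.4 steers sites toward a class with a member on the protocol's own QT list. For 41 of the 45 listed QT drugs, starting one on treatment leaves up to 21, 28 or 84 nominal days, depending on the phase, before an ECG is required.

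This rests on three things: the text as it stands, without the Investigator's Brochure; the general pharmacological fact that ondansetron is a 5-HT3 antagonist, since Appendix D does not state its class; and scheduled ECGs done on nominal days. The documents do not say how many patients would receive ondansetron. Exposure by that route could be anywhere from none to all patients treated for nausea, and the added QT risk cannot be estimated.

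**What to change.** - **Section 6.2.4:** state that, where possible, the anti-emetic should be on neither the QT table nor the CYP3A tables in Appendix D, nor on the current external QT list that Appendix D cites. The external list matters because the tables are not exhaustive.
- **Section 6.3.3:** state that Appendix D QT drugs should be avoided on treatment. If one cannot be avoided, extend the ECG monitoring instruction to it and give a timing, for example one ECG soon after starting. Do not carry over the dose reduction, which is there for CYP3A inhibitors.
- **Section 6.3.2:** make the Appendix D proviso consistent with this, so that it reads neither as a ban that contradicts 6.2.4 nor as silence on newly started drugs.

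The cost is a few sentences in the next amendment, with the ethics approval that section 10.1 requires and notice to about 40 sites. In practice it adds an occasional unscheduled ECG and a mild limit on anti-emetic choice. Sample size, endpoints and the SAP do not change.
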